B. Statistical Considerations

B.1. Sample Size Justification:

Our sample sizes were chosen based on an iterative process involving determining the size of the target population eligible, feasibility constraints, and then verifying adequate power to test the hypotheses across all of our proposed studies for Projects 1-5. Through these detailed considerations, and input from our expert statisticians, we have been able to verify adequate power to address all of our study aims with the proposed sample sizes for the SAGES I SELECT subsample (N=148), the SAGES II cohort (N=460) and the SAGES II subsample (N=180). Power has similarly been verified for all aims of each project. For SAGES II, approximately 50% of the cohort will be enrolled at BIDMC and 50% at BWH. The data, however, will be analyzed together. Computations allow for two-sided type-I error probability 0.05 and to take into account cumulative attrition consistent with our experience in this population. We use multiple imputation to account for missing data where appropriate.

B.1.2. Experimental design and sampling: general considerations

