Aim 2: To use mass cytometry (CyTOF) to characterize circulating immune cells associated with delirium and LTCD, and then validate these findings in an independent sample. Sample Size Justification: We base the power analysis for this aim on the pilot study of 7 non-delirious patients with percent of cell types CD45+CD11c+CD14+monocytes to total number of cells, measured at PREOP and POD1. The median of the paired differences was 10.15 with range 10.07-15.19, and the mean was 10.62 with SD of 6.55. We plan to use 40 matched pairs. Since this observed mean paired difference is for the surgery effect and not the delirium effect, we use 50% of this difference as the clinically significant delirium effect. We also assume that the signal to noise ratio is similar for the delirium effect, thus SD is expected to be 6.55. With these assumptions, we obtain a power of 0.98 for H2A. For H2B, focused on LTCD, assuming a larger effect size of 60% of the observed surgical effect, we obtain a power estimate of 0.94. For H2C, the validation sample with 40 matched pairs from SAGES II, we consider a cell surface marker with a relative risk of 1.6 with delirium compared to no delirium. With type-I error at 0.05, we obtain a power estimate of 0.82.

Aim 3: To measure CRP and the Walston inflammatory index in banked plasma, and freshly collected plasma and CSF, from a probability sample of 148 SAGES I participants (SAGES I SELECT). Sample Size Justification: For Aim 3, we have 148 subjects, probability sampled for delirium (74 with and 74 without) and frequency matched for age and baseline GCP. The predictors are the measured levels of plasma inflammatory markers, and CSF inflammatory and AD biomarkers. The outcomes are delirium and LTCD. We use a relative risk of 1.5 as the threshold of clinical significance, and a type-I error of 0.05, and calculate 0.84 power for delirium and 0.80 for LTCD. Thus, we have very good power for this Aim.

Project 3

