Aim 3 Analysis: For H3A, the analytic strategy will be similar to that described in Aim 1 with measured levels of inflammatory proteins (and the inflammatory index) being the independent variables, and delirium and LTCD being the outcomes. We will examine plasma markers at PREOP, POD2, and LTFU, and CSF at one time point, LTFU. We anticipate seeing the lowest levels of inflammatory markers in the group without delirium and slow rates of LTCD, and the highest levels in those with delirium and faster rates of LTCD. We will perform multivariable analyses using generalized linear models with a log link for delirium incidence, and identity link for continuous LTCD. In H3B, to examine interactions with CSF AD biomarkers, we will select the most predictive inflammatory (IL-6, CRP, sTNFR1, or the inflammatory index) and AD biomarker (A β_{42} , t-tau, p-tau, or p-tau/A β_{42} ratio) and put both into the generalized linear model together. We expect significant independent effects of both inflammatory markers and CSF AD biomarkers on delirium and LTCD.

Project 3

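### Project 2 Aim 3 states its 0.80 power for LTCD at a relative risk of 1.5, but the planned LTCD model is continuous with an identity link, so the figure does not describe the planned test

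*Protocol*

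**What the plan says.** Protocol B.1.3, Project 2, Aim 3 describes the sample: "we have 148 subjects, probability sampled for delirium (74 with and 74 without) and frequency matched for age and baseline GCP". The predictors are inflammatory and AD marker levels. On outcomes it says "The outcomes are delirium and LTCD". One effect size serves both: "We use a relative risk of 1.5 as the threshold of clinical significance, and a type-I error of 0.05". From this the authors "calculate 0.84 power for delirium and 0.80 for LTCD" and judge power for the aim to be very good. Section B.1 sets the general rule: "Computations allow for two-sided type-I error probability 0.05".

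Protocol B.2.3, Project 2, Aim 3 Analysis names the multivariable models, "using generalized linear models with a log link for delirium incidence, and identity link for continuous LTCD". It opens by tying H3A to an earlier aim: "For H3A, the analytic strategy will be similar to that described in Aim 1 with measured levels of inflammatory proteins".

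**The concern.** A relative risk is the natural parameter of the log-link model for delirium. It is not a parameter of an identity-link model for a continuous outcome, where the marker coefficient is a difference in mean decline or slope. The power section gives no slope difference, standard deviation or correlation for LTCD in this aim. The analysis section gives no cut-off or event rate that would turn LTCD into an event. The power figure and the named model are therefore on different scales.

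This is not a detail left for the SAP, because the protocol fixes both the power figure and the model, and they do not fit together. At stake is whether a reader can tell from this paragraph what size of marker effect on LTCD the 148 patients can detect.

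**Working it through.** **Inputs from the protocol.** N = 148, 74 with and 74 without delirium; relative risk 1.5; two-sided alpha 0.05; stated LTCD power 0.80. Section B.1.2 says analyses were originally powered for 128 (64 per group), so both sizes are checked.

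**Step 1. Try to reproduce 0.80.** A relative risk needs a reference risk p0, and none is stated for LTCD in this aim. Suppose LTCD were dichotomised and compared between two equal marker groups of n each (an assumption), with p1 = 1.5 × p0. The normal approximation with p̄ = (p0 + p1)/2 is

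power = Φ{ [ |p1 − p0|·√n − 1.96·√(2p̄(1−p̄)) ] / √(p0(1−p0) + p1(1−p1)) }.

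| n per group | p0 | p1 | power |
|---|---|---|---|
| 74 | 0.40 | 0.60 | 0.69 |
| 74 | 0.453 | 0.679 | 0.80 |
| 74 | 0.50 | 0.75 | 0.89 |
| 64 | 0.481 | 0.721 | 0.80 |
| 64 | 0.50 | 0.75 | 0.84 |

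So 0.80 needs a reference-group risk of about 45% (74 per group) or 48% (64 per group). Neither is stated.

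**Step 2. Use decline rates the protocol gives elsewhere.** B.1.3, Project 3, Aim 3 (H3b) assumes LTCD in 70% of patients with delirium and 20% of those without. In a sample that is half delirious, overall risk is (0.70 + 0.20)/2 = 0.45. That is the overall risk, not the risk in the low-marker group. With equal marker groups and relative risk 1.5, (p0 + 1.5·p0)/2 = 0.45 gives p0 = 0.36 and p1 = 0.54. At 74 per group the power is 0.60, not 0.80.

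**Step 3. The planned continuous analysis.** For 80% power at two-sided 0.05, z(0.975) + z(0.80) = 1.96 + 0.84 = 2.80.

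- Two equal marker groups: d = 2.80 × √(2/n). For n = 74, d = 0.46; for n = 64, d = 0.50.
- Continuous marker (Fisher z): r = tanh(2.80/√(N − 3)). For N = 148, r = tanh(2.80/√145) = 0.23; for N = 128, r = tanh(2.80/√125) = 0.25.

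These are before covariate adjustment and attrition. Under assumed losses of 10%, 20% and 30% from 74 per group, the detectable d rises to about 0.49, 0.51 and 0.55.

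**Step 4. Compare with the protocol's other LTCD calculations.** B.1.3, Project 1 gives detectable slope differences between biomarker groups in the same SAGES I sample: d = 0.53 (Aim 2, H2b) and 0.50 to 0.55 (Aim 3, H3c). Step 3 agrees with these, allowing for unequal marker groups and the smaller original N.

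**The case against.** The strongest reply is that the relative risk is a working simplification. H3A refers back to Aim 1, whose H1B splits LTCD into faster and slower, and the Aim 3 text itself speaks of slow and faster rates. The protocol simplifies elsewhere for power purposes too, and analysing LTCD as continuous normally loses no power against a dichotomised version.

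The stated figures can also be approached. At 0.50 v 0.75, 64 per group gives 0.84, the delirium figure, and 58 per group (64 less about 10%) gives 0.80, the LTCD figure. Section B.1 says attrition was taken into account.

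Part of this stands. The 0.80 may well have come from a real calculation, and a reader who inferred that it has no basis at all would go too far. But the rates and the attrition are inferred. A 0.50 v 0.75 contrast between equal groups also implies an overall rate of (0.50 + 0.75)/2 = 62.5%, not the 50% of an even faster/slower split. The H1B split is defined for 60 delirium cases only, and its power rests on a difference in marker level rather than a relative risk. No cut-off or event rate is carried into Aim 3, where the only LTCD model named is continuous.

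A reader might also infer that the detectable LTCD effect is unknown. That is not supported either: the Project 1 figures in step 4 give it in substance for biomarker groups in the same sample. What is missing is its statement for this aim.

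**Conclusion.** The point holds as a mismatch between a stated power figure and the model named for the same outcome. The 0.80 for LTCD is on a scale the planned analysis does not estimate, and the stated inputs do not reproduce it. The 45% and 48% reference risks and the power of about 0.60 rest on two assumptions: a dichotomised outcome and two equal marker groups.

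A reader might infer that the aim is underpowered; the documents do not show this. At d = 0.48, the delirium effect on slope quoted in Project 1 (not a marker effect), power with 74 per group would be about 0.83 before attrition, and about 0.79 and 0.74 under assumed losses of 10% and 20%. No single corrected power can be given, because the protocol states no expected marker effect on LTCD for this aim. Section B.1 describes sample sizes set by the eligible population and feasibility, with power then verified, so the error affects the justification rather than the design.

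**What to change.** In B.1.3, Project 2, Aim 3, replace the relative-risk-based 0.80 for LTCD with the effect detectable by the planned continuous model at 80% power and two-sided 0.05: r of about 0.23, or about 0.46 SD between two equal marker groups, at N = 148 (about 0.25 and 0.50 SD at N = 128). Recompute it for the number expected to have LTCD data, and keep it in line with the 0.50 to 0.55 SD given in Project 1.

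If a binary LTCD outcome is really intended, define it with its cut-off and event rate and amend the Aim 3 analysis text to match. The first option costs one restated figure and changes nothing in the sample or the data collection.

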Aim 1: Determine in people with evidence of preclinical AD whether AD-related brain atrophy or network dysfunction are associated with delirium, delirium severity, or LTCD. Power Analysis: For H1a, the SAGES II MRI sample has 180 subjects. We expect 32% to have abnormal CSF AD biomarkers⁶⁵ (n=57). Based on published rates⁶⁶, we expect 36% of the AD biomarker positive sample to develop delirium. From our previous studies, the mean of AD-signature cortical thickness is 2.49mm (SD 0.14). We assume this distribution for the non-delirium patients. A conservative effect size of 5%

decrease in cortical thickness for the delirium patients yields a mean of 2.37mm. With type-I error of 0.05, we obtained a power estimate of 0.87. For H1b, the SAGES I SELECT cohort has 148 patients. With 34% assumed to have abnormal CSF AD biomarkers, this yields 44 subjects. We assume that for those without delirium and no LTCD, cortical thickness has the same distribution as stated above and that those with both delirium and LTCD would have even greater atrophy than delirium alone; thus a slightly increased but still conservative threshold of 7% decrease yields 2.37mm. The power estimate is 0.97 given this sample and relative difference of the two cortical thickness means. For H1c, the combined sample size would be 48+44=92. The estimated pairwise Spearman correlation coefficient among the MRI and CSF biomarker variables would be statistically significantly detected at the level of correlation equal to at least 0.4 from the null estimate of 0.1, and power of 0.87.

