Aim 2. Determine in people without evidence of preclinical AD whether vulnerable aging-related brain atrophy or network dysfunction are associated with delirium, delirium severity, or LTCD. Power Analysis: We expect 68% of the 180 SAGES II subjects for H2a will have normal CSF AD biomarkers, yielding a sample size of 123. Among these, we expect 24% with delirium (30 with delirium, 93 without). From prior work,⁶⁷ we assume that the Aging-signature cortical thickness for the power analysis is 1.94mm (SD 0.18) for the non-delirium patients. A conservative effect size of 6% decrease in cortical thickness for the delirium patients yields a mean of 1.82 mm. With type-I error of 0.05, we obtained a power estimate of 0.88. For H2b, the SAGES I SELECT cohort has 148 patients. With 66% assumed to have normal CSF AD biomarkers, this yields 88 subjects. We assume that for those without delirium and no LTCD, vulnerable aging cortical thickness has the same distribution as stated above and that those with both delirium and LTCD would have even greater atrophy than delirium alone; thus a slightly increased but still conservative threshold of 7% decrease yields 1.80mm. The power estimate is 0.94 given this sample and the effect size of 7% in relative difference of the two cortical thickness means. For H2c, the combined sample size would be 123+84=207. The estimated pairwise Spearman correlation coefficient among the inflammatory biomarkers from Project 2 and the vulnerable aging MRI variables would be statistically significantly detected at the level of correlation equal to at least 0.3 from the null estimate of 0.1, and the power of 0.85. At the correlation level of 0.3, power is 0.85.

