Aim 1 Analysis: For this aim, we will restrict the sample to only those subjects who have abnormal CSF or PET AD biomarkers. For H1a, we will use 2 GLM models, one for delirium incidence (log link), and one for delirium severity (identity link). The independent variables for these models are the variables from domain 2 (AD cortical thickness, memory network connectivity, hippocampal hyperactivity). Included in these GLM models are also potential confounders of demographic and baseline clinical variables. The estimated coefficients and 95% confidence intervals will allow us to assess the independent adjusted effects of this domain on delirium outcomes in this cohort of patients with abnormal preclinical AD biomarkers. We will estimate goodness-of-fit of these models by checking model residuals, estimates of the area under the ROC curve, and adjusted model R² values. For H1b, the four variables from domain 2 will be treated as independent variables in a Generalized Linear Mixed model with identity link, and the dependent variables in this model will be the longitudinal GCP values. In this model, delirium status, and the interaction between GCP and delirium status are also included. This model allows the estimation of the association (slope) between domain 2 variables, and GCP-based long term cognitive decline modified by delirium status. For H1c, we will report the correlation matrix using the nonparametric Spearman correlation coefficients for pairwise correlation among the variables of domains 2 and 4 (A β , p-tau, t-tau, NFL).

Aim 2 Analysis and Statistical Power: For this aim, we will restrict the sample to only those subjects who have normal CSF or PET AD biomarkers. The statistical approach for H2a and H2b is the same as described for Aim 1 but the independent variables for these models are the variables from domain 4 (vulnerable aging cortical thickness, frontoparietal functional and structural connectivity). For H2c, we will report the correlation matrix using the nonparametric Spearman correlation coefficients for pairwise correlation among domain 4 variables and the inflammatory biomarker variables found in Project 2.

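### Project 3 H1c and H2c pool SAGES I SELECT and SAGES II in one Spearman matrix with no cohort term, so a cohort difference in both the MRI measure and the marker can create or mask a correlation

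*Protocol*

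**What the plan says.** Section B.1.3 (Power by Project), Project 3, sizes both correlation hypotheses on the sum of the two cohorts. Aim 1 states: "For H1c, the combined sample size would be 48+44=92". It claims detection "at the level of correlation equal to at least 0.4 from the null estimate of 0.1, and power of 0.87". Aim 2 states: "For H2c, the combined sample size would be 123+84=207", with detection "at the level of correlation equal to at least 0.3 from the null estimate of 0.1, and the power of 0.85". Section B.1 sets the error level: "Computations allow for two-sided type-I error probability 0.05".

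Section B.2.3 (Data Analysis by Project), Project 3, fixes the statistic. Aim 1: "For H1c, we will report the correlation matrix using the nonparametric Spearman correlation coefficients for pairwise correlation among the variables of domains 2 and 4". Aim 2 likewise plans Spearman coefficients for "pairwise correlation among domain 4 variables and the inflammatory biomarker variables found in Project 2". Neither sentence mentions cohort. In the same section, the H1a models do include potential confounders.

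**The concern.** The two cohorts are not two draws from one population measured in one way:

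- **Age and timing.** SAGES I patients were 70 or older at surgery (A.3.1). SELECT is measured about four years later (A.2.3), so at roughly 74 or older. SAGES II enrolls from 65 (A.4), and its MRI and CSF are planned before surgery (A.2.3).
- **Delirium.** SELECT is 50% by sampling (74 of 148). In SAGES II, Project 3 expects 24% among biomarker-normal and 36% among biomarker-positive patients (B.1.3).
- **CSF.** SELECT gives 10-15 ml at a research lumbar puncture, with the first 1-2 ml discarded (A.3.2.3). SAGES II gives 2.0 ml at spinal anesthesia (A.4.8).

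Project 3 sets out to link imaging markers to molecular markers. If cohort membership moves both, part of a pooled rank correlation reflects cohort rather than that link. Equal-direction shifts can produce a significant result without a matching association inside either cohort, and opposite shifts can conceal one that exists. The H2c imaging variable is an aging signature, so age is a plausible route for such a shift.

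**Working it through.** **1. Reproduce the stated power.** Inputs from B.1.3: N = 92, 0.4 against 0.1, stated power 0.87 (H1c); N = 207, 0.3 against 0.1, stated power 0.85 (H2c); two-sided 0.05. Single-sample Fisher z: power = Φ[(atanh r1 − atanh r0)·√(N − 3) − 1.96].

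- H1c: (0.4236 − 0.1003)·√89 = 3.05, power 0.862.
- H2c: (0.3095 − 0.1003)·√204 = 2.99, power 0.848.

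Both lie within about a point of the stated values. One-sided versions give 0.920 and 0.910 and do not fit. The power text therefore treats each total as one homogeneous sample.

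**2. What pooling does to the coefficient.** Let p be one cohort's share, ρ the correlation inside each cohort, and dx and dy the cohort shifts in SD units. For normal data and shifts of equal size d in the same direction, pooled r = [ρ + p(1 − p)d²] / [1 + p(1 − p)d²]. With opposite directions the term in the numerator is subtracted. In general that term is p(1 − p)·dx·dy, so a shift in only one variable creates no correlation.

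For H2c, p = 123/207 = 0.594 and p(1 − p) = 0.241. With ρ = 0:

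- d = 0.25: 0.0151/1.0151 = 0.015
- d = 0.5: 0.0603/1.0603 = 0.057
- d = 0.75: 0.1356/1.1356 = 0.119
- d = 1.0: 0.241/1.241 = 0.194

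**3. Error rates by simulation.** Normal data, the protocol's group sizes, Fisher z with Spearman variance 1.06/(n − 3), 6,000 to 10,000 replicates. The shifts are assumptions. Two-sided rejection of zero when ρ = 0:

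| Shift in both | H2c pooled | H1c pooled | Stratified |
|---|---|---|---|
| 0.5 SD | 11% | 8% | 4-5% |
| 0.75 SD | 37% | 20% | 4-5% |
| 1.0 SD | 79% | 47% | 4-5% |

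At 0.25 SD the H2c rate is about 5%.

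Against the protocol's own null, with ρ = 0.1 inside each cohort, pooled H2c rejects in about 9% at 0.5 SD and 30% at 0.75 SD. At 0.3 SD, upper-tail rejection (nominal 2.5%) is 3.5% for H2c and 2.8% for H1c. The stratified estimate stays near 2% in that tail.

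**4. Masking.** With the planned alternative true and opposite shifts of 0.5 SD, pooled power falls from about 0.79 to 0.48 (H1c) and from about 0.78 to 0.37 (H2c). Stratified power stays at about 0.77 to 0.79. These start below the figures in step 1 because the simulation uses the Spearman statistic and its larger variance.

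**5. Cost of stratifying.** With weights n − 3 per cohort, N − 3 becomes N − 6.

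- H1c: 0.3233·√86 = 3.00, power 0.850 against 0.862.
- H2c: 0.2092·√201 = 2.97, power 0.843 against 0.848.

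**6. The only shift the documents let one derive.** H2a assumes thickness of 1.94 mm without and 1.82 mm with delirium, SD 0.18, a gap of 0.12/0.18 = 0.67 SD. If SELECT's 50% delirium share also holds among its biomarker-normal patients, the mix alone moves mean thickness by (0.50 − 0.24)·0.67 = 0.17 SD. That is below the level at which pooling matters, so a material bias would need age, timing or sampling to add to it.

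**7. Counts.**

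- SAGES II biomarker-positive: 57 in H1a (0.32·180 = 57.6), but 48 in H1c.
- SELECT biomarker-normal: 88 in H2b, but 84 in H2c.
- SELECT shares: 34% and 66% of the stated 148 are 50.3 and 97.7, not 44 and 88. On the earlier size of 128 they are 43.5 and 84.5, which fits 44 and 84.

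**The case against.** The strongest reply is that the pooling stands in the power text, while the analysis text only promises a correlation matrix and does not say that the cohorts are merged. Cohort handling in a largely descriptive matrix could be left to a statistical analysis plan. B.2.1 also says that covariates will be chosen for confounding potential and promises sensitivity analyses. This carries some weight, but the covariate text concerns models, and a raw Spearman matrix has no place for a covariate. The protocol has chosen both the statistic and the combined sample.

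The second reply is that the harm is assumed. This stands in part. No cohort shift is given. Some features could narrow or offset one: each aim is restricted to one AD-biomarker status, the SAGES II imaging subgroup is enriched to 25% MCI against 19 of 128 (15%) in SAGES I, and CSF is handled alike after collection. The choice of null matters too. If the within-cohort correlation is truly zero and the test is against 0.1, H2c rejects in only 0.4% at 0.5 SD, 4% at 0.75 SD and 27% at 1 SD.

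Third, B.1.2 explains that power was first computed for 128 SAGES I patients. That accounts for 44 and 84, but not for 88, nor for 48 against 57.

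Finally, adjusting an aging signature for age may remove the signal that H2c seeks. That is a fair limit on the remedy.

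**Conclusion.** The point holds as a risk of bias built into the planned statistic. Cohorts that differ by design are pooled with no cohort term, and the pooled coefficient can then overstate or understate the association. For H2c, equal shifts give a two-sided error of about 10% at 0.5 SD and 30 to 37% at 0.75 SD, depending on the null. At about 0.25 to 0.3 SD the effect is negligible. These figures rest on normal data and on assumed shifts in both variables.

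A reader might infer that the planned correlations will be spurious. The documents do not support that: they give no shift, and the one that can be derived, from delirium mix, is about 0.17 SD in thickness. A reader might also infer that the power is wrong. It is not: the stated values reproduce closely for the totals used, and the defect is bias, not sample size. Nor are all the odd counts fresh errors, since two are carried over from the superseded size of 128.

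**What to change.** In B.2.3, Project 3, Aims 1 and 2, state that H1c and H2c will be computed as Spearman correlations within each cohort, with both shown, and combined on the Fisher-z scale with weights n − 3. A partial Spearman adjusted for cohort would also serve. Keep age adjustment as a sensitivity analysis only. Change the power text in B.1.3 to match.

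The cost is a few sentences and a few lines of code, with no extra patients or data, and 0.5 points of power for H2c and 1.2 for H1c. Showing both cohorts also reveals whether an association replicates.

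Separately, reconcile 48 with 57, 84 with 88, and 44 and 88 with their stated shares of 148, then restate sizes and power on one base. On 148 and 180 the shares give 123 + 98 = 221 for H2c. For H1c, 57 + 50 = 107 is only a ceiling: patients who receive amyloid PET instead of CSF sampling have no CSF tau or NFL value, so the H1c size should count only those expected to have CSF.

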Aim 3. Investigate whether cortical atrophy due to preclinical AD or vulnerable aging is associated with postoperative LTCD or delirium with LTCD. Power Analysis: For H3a, using estimates from prior work,⁶⁷ the estimated mean prevalence of cortical atrophy of either preclinical AD or aging is 19.3%. We assume this estimate for the no delirium group, and a relative risk of 2.5 of having cortical atrophy for the delirium group. Of the 126 subjects, 22% (n=28) subjects had delirium, and 98 did not. Given these estimates, the power is 0.82. For H3b, among those with delirium and LTCD relative to those with no delirium, and no LTCD, we assume that the conditional probability of having LTCD given that one has delirium is 70%, and the conditional probability of having LTCD given that one does not have delirium is 20%. Given these estimates, the joint frequency distribution is N=20 for those with both conditions of delirium and LTCD, and N=78 for those with neither condition. The expected relative risk would be higher in this comparison than 2.5 in H3a. With a power of 0.81, and the given sample size of 126, we could detect a statistically significant relative risk of at least 2.75 at type-I error of 0.05.

Project 4

Aim 1a: Mount a Modified Delphi Process Involving Delirium Experts to Identify Predictors of Delirium and Cognitive Decline Following Delirium (Complicated Delirium) for Early Identification. Statistical Power Considerations: N/A

Aim 1b. Operationalize and Evaluate the Accuracy of the Predictors for Complicated Delirium. Statistical Power Considerations. Our pilot data suggest we might expect a correlation between model-implied cognitive slope and observed cognitive slope of about r = .54. With 375 patients in the model development sample and 185 in the model testing sample, we used Monte Carlo procedures to determine that we will have an 80% probability of obtaining a correlation between .48 and .60 in both the model development and model testing samples. Therefore, we believe this aim is adequately powered to generate a reasonable probability of identifying a replicable model.

Aim 2a: Identify and Cross-Validate Predictors of Complicated Delirium. Statistical Power

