Aim 3 Analysis and Statistical Power: We will estimate the association between cortical atrophy due to either preclinical AD or vulnerable aging and LTCD (i.e. longitudinally measured GCP). We will treat atrophy as a binary outcome variable in the multivariable GLM model with log link, and repeated GCP measurements as independent variables. We will estimate the slope of GCP at each follow-up time point. In the event that we have high correlation among the GCP measurements, we will make use of the distributed lag model to mitigate the collinearity problem. For H3b, we will add to this GLM model from H3a, delirium status (binary), and the interaction between GCP and delirium status, and will obtain GCP slope conditioning on delirium status.

Project 4

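### Project 3 H3a: the stated power of 0.82 is for atrophy in delirium v no delirium, and none is shown for atrophy v long-term cognitive decline

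*Protocol*

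**What the plan says.** Protocol B.1.3, Project 3 Aim 3, states the aim as whether cortical atrophy is associated with postoperative LTCD, or with delirium accompanied by LTCD. A.2.3 names the same two outcomes.

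The H3a power calculation in B.1.3 uses these inputs:
- Without delirium, "the estimated mean prevalence of cortical atrophy of either preclinical AD or aging is 19.3" per cent.
- The effect is "and a relative risk of 2.5 of having cortical atrophy for the delirium group".
- The groups are defined by delirium: "Of the 126 subjects, 22% (n=28) subjects had delirium, and 98 did not".
- The result: "Given these estimates, the power is 0.82".

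For H3b the same paragraph brings in LTCD for the first time: "we assume that the conditional probability of having LTCD given that one has delirium is 70" per cent, against 20% without delirium. This gives 20 patients with both conditions and 78 with neither.

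The analysis in B.2.3, Project 3 Aim 3, reads "We will estimate the association between cortical atrophy due to either preclinical AD or vulnerable aging and LTCD (i.e. longitudinally measured GCP"). Atrophy is the binary outcome of a log-link model and the repeated GCP measurements are the predictors. Delirium status and its interaction with GCP are added to that model only for H3b.

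B.1 sets the general conditions ("Computations allow for two-sided type-I error probability 0.05") and says that power has been checked for the aims of every project.

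**The concern.** The H3a calculation contains no LTCD quantity. Its exposure is delirium, and delirium is not in the H3a model. The association that H3a appears to test, atrophy against LTCD, has neither an assumed effect nor a power.

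This is not a detail left for a statistical analysis plan. The protocol prints a power and attaches it to a different comparison. A reader of B.1.3 would take H3a to be powered at 82% when no calculation for it is shown. A null result for atrophy v LTCD could then be read as coming from a well-powered test.

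**Working it through.** **Inputs, all from B.1.3 Project 3 Aim 3 except alpha (B.1).** Two-sided alpha 0.05. N = 126, of whom 28 had delirium and 98 did not. Atrophy is 19.3% without delirium and 0.193 × 2.5 = 48.25% with delirium. P(LTCD) is 70% with delirium and 20% without.

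**Step 1: reproduce 0.82.** Comparing 48.25% of 28 with 19.3% of 98, exact enumeration with Fisher's test gives 0.822. The arcsine approximation gives 0.832 and the pooled normal 0.849. The stated figure is right for delirium v no delirium. The same Fisher method gives 0.815 for the H3b figure of 0.81 (20 v 78, risk ratio 2.75).

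**Step 2: build the LTCD groups.**
- With LTCD: 0.70 × 28 + 0.20 × 98 = 19.6 + 19.6 = 39.2.
- Without LTCD: 126 − 39.2 = 86.8, of whom 8.4 had delirium and 78.4 did not.

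**Step 3: atrophy by LTCD if it depends on delirium only.**
- With LTCD: (19.6 × 0.4825 + 19.6 × 0.193) / 39.2 = 0.338.
- Without LTCD: (8.4 × 0.4825 + 78.4 × 0.193) / 86.8 = 0.221.
- Risk ratio: 0.338 / 0.221 = 1.53.

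Power (pooled normal) = Φ[(difference − 1.96 × SE0) / SE1]. The overall rate is (28 × 0.4825 + 98 × 0.193) / 126 = 0.257.
- SE0 = √[0.257 × 0.743 × (1/39.2 + 1/86.8)] = 0.084.
- SE1 = √[0.338 × 0.662/39.2 + 0.221 × 0.779/86.8] = 0.088.
- Power = Φ[(0.117 − 0.165) / 0.088] = 0.29.

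With the rounded cells (40 v 86) power is 0.30, or 0.25 with Fisher's test.

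**Step 4: let LTCD carry its own atrophy risk.** The table uses the rounded cells (20, 8, 20, 78) and the pooled normal method. Rows 1 to 6 keep the atrophy rate in each delirium group at 48.25% and 19.3%.

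| Assumption about atrophy and LTCD | Power |
|---|---|
| No link within delirium groups | 0.30 |
| Risk ratio 2.75 in the delirium-plus-LTCD cell only | 0.45 |
| Within-group risk ratio 1.25 | 0.51 |
| Within-group risk ratio 1.5 | 0.68 |
| Within-group risk ratio 1.75 | 0.81 |
| Within-group risk ratio 2.0 | 0.89 |
| Risk ratio 2.5 applied directly to LTCD, 19.3% without LTCD | 0.91 |

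In the last row, holding overall atrophy at 25.7% instead gives 0.86.

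**Step 5: a version that does not dichotomise LTCD.** For a two-group comparison of GCP slope by atrophy status, the detectable difference at 80% power is d = 2.80 × √(1/n1 + 1/n2).
- 25.7% atrophy (32.4 v 93.6): d = 0.57 SD.
- 19.3% atrophy (24.3 v 101.7): d = 0.63 SD.

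This is an approximation, because B.2.3 makes atrophy the outcome and GCP the predictor.

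**The case against.** A reader might infer that the protocol's own rates imply a power of about 0.29 for H3a. The documents do not support that. No atrophy rate is given by LTCD status, and the 70% and 20% rates are stated for H3b only. The 0.29 needs atrophy to be independent of LTCD within each delirium group. Under that assumption, delirium with LTCD v neither has a risk ratio of exactly 48.25 / 19.3 = 2.5, whereas B.1.3 expects it to exceed 2.5. Aims 1 and 2 of Project 3 likewise assume more atrophy with delirium and LTCD together than with delirium alone. The 0.29 is the low end of the range. It also splits LTCD into yes and no, which the planned model does not do.

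Three further points are fair. The H3a hypothesis is not printed, so its content is inferred from the aim and the analysis section. The 126 are SAGES I patients who already have longitudinal MRI, so this figure did not set recruitment. And the 0.82 is correct for the contrast it describes.

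These points limit the size of the finding but do not remove it. The aim, A.2.3 and B.2.3 all point to atrophy v LTCD, and the H3b calculation fits that reading. The power printed for H3a still concerns a different exposure.

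**Conclusion.** The point holds as a mismatch between the stated power and the analysis. The 0.82 is for atrophy in 28 patients with delirium v 98 without, and no power is shown for atrophy v LTCD, so the general statement in B.1 is not borne out for H3a.

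The size cannot be fixed from the protocol. In a simplified comparison of about 39 patients with LTCD and 87 without, power runs from about 0.3 to 0.9. The assumed delirium effect alone does not bring H3a to 80%. A further within-group risk ratio of about 1.75 for LTCD would be needed, and the protocol neither states nor justifies one. These figures are illustrations that rest on the 70% and 20% rates, on the atrophy rates assumed for delirium, and on a binary LTCD. They do not show that H3a is underpowered.

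**What to change.** In B.1.3, Project 3 Aim 3:

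1. Relabel the 0.82 as power for atrophy in delirium v no delirium, and stop presenting it as the H3a power.
2. State a power or detectable effect for atrophy v LTCD in the 126 patients, with the assumed atrophy rate and the assumed association with LTCD written out. A figure on the scale of the B.2.3 model (binary atrophy regressed on GCP) would match the analysis. If the simpler slope comparison is used (about 0.57 to 0.63 SD at 80% power), say that it is an approximation that reverses outcome and predictor.
3. If LTCD is treated as binary, show the range across assumptions and not a single value.
4. Print the H3a and H3b hypotheses, so that each power can be matched to its test.

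The cost is a few lines of text and a short calculation. Sample size, data collection and the planned model are unaffected.
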